6.2 Adverse Events

6.2.1 Definitions

- Adverse Event (AE): Any untoward medical occurrence (including laboratory findings) associated with study procedures, the use of a device, biologic in a study participant, including any comparator used, irrespective of the relationship between the adverse event and the device(s) under investigation (referred to as *Adverse Reaction* when caused by a drug).
- 610 Serious Adverse Event (SAE): Any untoward medical occurrence that meets at least one of the following:
- Results in death.

585

586

587

588

589

590

591 592

593

604

- Is life-threatening; (a non-life-threatening event which, had it been more severe, might have become life-threatening, is not necessarily considered a serious adverse event).
- Requires inpatient hospitalization or prolongation of existing hospitalization.
- Results in persistent or significant disability/incapacity or substantial disruption of the ability to conduct normal life functions (sight threatening).
- Is a congenital anomaly or birth defect.
- Is considered a significant medical event by the investigator based on medical judgment (e.g., may jeopardize the participant or may require medical/surgical intervention to prevent one of the outcomes listed above).
- 621 Unanticipated Adverse Device Effect (UADE): Any serious adverse effect on health or safety or any
- 622 life -threatening problem or death caused by, or associated with, a device, if that effect, problem, or death
- was not previously identified in nature, severity, or degree of incidence in the investigational plan or

- application (including a supplementary plan or application), or any other unanticipated serious problem
- associated with a device that relates to the rights, safety, or welfare of participants (21 CFR 812.3(s)).
- 626 Adverse Device Effect (ADE): Any untoward medical occurrence in a study participant which the device
- may have caused or to which the device may have contributed (Note that an Adverse Event Form is to be
- 628 completed in addition to a Device Issues Form, unless excluded from reporting as defined in section
- 629 6.2.2).

- 630 Comparator: Medical device, therapy (e.g. active treatment, normal clinical practice), placebo or no
- treatment, used in the control group in a clinical investigation. (ISO 14155:2020)
- 632 Device Complaints and Malfunctions: A device malfunction or complaint is something that happens
- to a device or related to device performance, whereas an adverse event happens to a participant. A device
- complaint may occur independently from an AE, or along with an AE. An AE may occur without a
- device complaint or there may be an AE related to a device complaint. A device malfunction is any
- failure of a device to meet its performance specifications or otherwise perform as intended.
- Performance specifications include all claims made in the labeling for the device. The intended
- 638 performance of a device refers to the intended use for which the device is labeled or marketed.
- 639 (21 CFR 803.3). Note: for reporting purposes, sites will not be asked to distinguish between device
- 640 complaints and malfunctions.
- 641 Use Error: User action or lack of user action while using the medical device (3.34) that leads to a
- different result than that intended by the manufacturer or expected by the user. Includes the inability of
- the user to complete a task. Use errors can result from a mismatch between the characteristics of the user,
- user interface, task or use environment. Users might be aware or unaware that a use error has occurred.
- An unexpected physiological response of the patient is not by itself considered a use error. A malfunction
- of a medical device that causes an unexpected result is not considered a use error. (ISO 14155:2020)

6.2.2 Reportable Adverse Events

- A reportable adverse event includes all events meeting the definition of an adverse event, except for the following:
- Hypoglycemia and hyperglycemia not meeting the criteria below will not be recorded as adverse events unless associated with an Adverse Device Effect or discontinuation of the study device.
- Skin reactions from sensor or pump infusion set placement are only reportable if severe and/or required treatment.

- All reportable AEs—whether volunteered by the participant, discovered by study personnel during
- questioning, or detected through physical examination, laboratory test, or other means—will be reported
- on an AE form online. Each AE form is reviewed by the Medical Monitor to assess safety and to verify
- the coding and the reporting that is required.

659 660

661

662

663

664

665

666

667

668

669

670

671

677

6.2.3 Hypoglycemic Events

Hypoglycemia is only reportable as an adverse event when one of the following criteria is met:

- a hypoglycemic event occurred meeting the following definition of severe hypoglycemia: the event required assistance of another person due to altered consciousness, and required another person to actively administer carbohydrate, glucagon, or other resuscitative actions. This means that the participant was impaired cognitively to the point that he/she was unable to treat himself/herself, was unable to verbalize his/ her needs, was incoherent, disoriented, and/or combative, or experienced seizure or loss of consciousness. These episodes may be associated with sufficient neuroglycopenia to induce seizure or loss of consciousness. If glucose measurements are not available during such an event, neurological recovery attributable to the restoration of glucose to normal is considered sufficient evidence that the event was induced by a low glucose concentration.
- evaluation or treatment was obtained at a health care provider facility for an acute event involving hypoglycemia, or the participant contacted the site and received guidance following the occurrence of an acute event involving hypoglycemia
- When a severe hypoglycemia event occurs (as defined above), an Adverse Event Form should be
- completed. Severe hypoglycemia events should be considered to be serious adverse events with respect to
- reporting requirements. When a severe hypoglycemia event occurs during use of a study device, it
- generally will be considered to be unrelated to the device (per section 6.2.5) if the device functioned as
- intended and there does not appear to be a flaw in how the device is intended to function.

6.2.4 Hyperglycemic/Ketotic Events

- 678 Hyperglycemia is only reportable as an adverse event when one of the following criteria is met:
- the event involved DKA, as defined by the Diabetes Control and Complications Trial (DCCT) and described below
- evaluation or treatment was obtained at a health care provider facility for an acute event involving hyperglycemia or ketosis, or the participant contacted the site and received guidance on how to manage the hyperglycemia/ketosis
- blood ketone level ≥1.0 mmol/L, even if there was no communication with a health care provider at the time of the event
- Hyperglycemic events are classified as DKA if all of the following are present, or judged likely to have been present based on available data:
- Symptoms such as polyuria, polydipsia, nausea, or vomiting;
- Serum ketones > 1.5 mmol/L or large/moderate urine ketones;
- Either arterial blood pH <7.30 or venous pH <7.24 or serum bicarbonate (or CO2) <15; and
- Treatment provided in a health care facility
- When a hyperglycemia/ketotic event qualifies as an AE, or as a SAE as defined in section 6.2.1, an
- 693 Adverse Event Form should be completed. Events meeting DKA criteria should be considered to be
- serious adverse events with respect to reporting requirements. Hyperglycemia events not meeting criteria

- 695 for DKA generally will not be considered as serious adverse events unless one of the SAE criteria in
- section 6.2.1 is met.

- When a hyperglycemia/DKA event occurs during use of a study device, it generally will be considered to
- be unrelated to the device (per section 6.2.5) if the device functioned as intended and there does not
- appear to be a flaw in how the device is intended to function.

6.2.5 Relationship of Adverse Event to Study Investigational Device

- The study investigator will assess the relationship of any adverse event to the study device or study drug.
- The Medical Monitor also will make this assessment, which may or may not agree with that of the study
- 703 investigator. Reporting requirements will be based on the Medical Monitor's assessment.
- To ensure consistency of adverse event causality assessments, investigators should apply the following
- general guidelines when determining whether an adverse event is related to a study device or study drug:
- 706 Unrelated: The AE is clearly not related to a study drug/device and a likely alternative etiology exists
- such as an underlying disease, environmental or toxic factors or other therapy.
- 708 Unlikely Related: The AE does not follow a reasonable temporal sequence during or after use of study
- drug/device and a more likely alternative etiology exists such as an underlying disease, environmental or
- 710 toxic factors, or other therapy.
- Possibly Related: The AE occurred in a reasonable time during or after use of study drug/device; but
- could be related to another factor such as an underlying disease, environmental or toxic factors, or other
- therapy; and there is a possible, though weak, scientific basis for establishing a causal association
- between the AE and the study drug/device.
- 715 **Probably Related:** The AE occurred in a reasonable time during or after use of study drug/device; is
- 716 unlikely to be related to another factor such as an underlying disease, environmental or toxic factors, or
- other therapy; and there is a plausible, though not strong, scientific basis for establishing a causal
- association between the AE and the study drug/device.
- 719 **Definitely Related:** The AE occurred in a reasonable time during or after use of study drug/device;
- cannot be explained by another factor such as an underlying disease, environmental or toxic factors, or
- 721 therapy; and there is a strong scientific basis for establishing a causal association between the AE and the
- study drug/device.
- Events determined to be *Possibly Related*, *Probably Related*, or *Definitely Related* will be considered
- 'Related' with respect to any required IRB and FDA reporting.

6.2.6 Severity (Intensity) of Adverse Events

- The severity (intensity) of an adverse event will be rated on a three-point scale: (1) mild, (2) moderate,
- or (3) severe. A severity assessment is a clinical determination of the intensity of an event. Thus, a severe
- adverse event is not necessarily serious. For example, itching for several days may be rated as severe, but
- may not be clinically serious.
- 730 MILD: Usually transient, requires no special treatment, and does not interfere with the participant's daily
- 731 activities.

- MODERATE: Usually causes a low level of inconvenience, discomfort or concern to the participant
- and may interfere with daily activities, but is usually ameliorated by simple therapeutic measures and
- participant is able to continue in study.
- 735 SEVERE: Interrupts a participant's usual daily activities, causes severe discomfort, may cause
- discontinuation of study device, and generally requires systemic drug therapy or other treatment.

6.2.7 Expectedness

737

741

743

754

755

756 757

766

For a serious adverse event that is considered possibly related to study device, the Medical Monitor will classify the event as unexpected if the nature, severity, or frequency of the event is not consistent with the risk information previously described in the protocol, labeling, or Investigator Brochure.

6.2.8 Coding of Adverse Events

Adverse events will be coded using the MedDRA dictionary.

6.2.9 Outcome of Adverse Events

The outcome of each reportable adverse event will be classified by the investigator as follows:

- RECOVERED/RESOLVED The participant recovered from the AE/SAE without sequelae. Record the AE/SAE stop date.
- RECOVERED/RESOLVED WITH SEQUELAE The event persisted and had stabilized without change in the event anticipated. Record the AE/SAE stop date.
- FATAL A fatal outcome is defined as the SAE that resulted in death. Only the event that was the cause of death should be reported as fatal. AEs/SAEs that were ongoing at the time of death; however, were not the cause of death, will be recorded as "resolved" at the time of death.
- NOT RECOVERED/NOT RESOLVED (ONGOING) An ongoing AE/SAE is defined as the event was ongoing with an undetermined outcome.

An ongoing outcome will require follow-up by the site in order to determine the final outcome of the AE/SAE. The outcome of an ongoing event at the time of death that was not the cause of death, will be updated and recorded as "resolved" with the date of death recorded as the stop date.

- UNKNOWN An unknown outcome is defined as an inability to access the participant or the participant's records to determine the outcome (for example, a participant that was lost to follow-up).
- 760 If any reported adverse events are ongoing when a participant completes the study (or withdraws),
- adverse events classified as UADEs or related SAEs or SUSARs will be followed until they are either
- 762 resolved, or have no prospect of improvement or change, even after the participant has completed all
- applicable study visits/contacts. For all other adverse events, data collection will end at the time the
- participant completes the study. Note: participants should continue to receive appropriate medical care
- for an adverse event after their participation in the study ends.

6.3 Reportable Device Issues

- All UADEs and ADEs as defined in section 6.2.1 will be reported as both 'device issues' and adverse events, except for skin reactions from CGM sensor placement or pump infusion set placement that do not require pharmacologic treatment.
- Device issues will be reported except in the following circumstances. These occurrences are expected and will not be reported on a Device Issue Form assuming criteria for a UADE or ADE have not been met:
- CGM sensor lasting fewer days than expected per manufacturer
- CGM tape adherence issues
- Pump infusion set insertion lasting fewer days than expected per manufacturer
- Battery lifespan deficiency due to inadequate charging or extensive wireless communication

- Intermittent device component disconnections/communication failures not requiring system replacement or workaround/resolution not specified in user guide/manual.
- Device issues clearly addressed in the user guide manual that do not require additional troubleshooting

6.4 Timing of Event Reporting

- SAEs possibly related to a study device, study drug, or study participation and UADEs must be reported
- by the site to the Sponsor within 1 working day of the site becoming aware of the event. This can occur
- via phone or email, or by completion of the appropriate eCRFs as applicable. If the form(s) are not
- initially completed, they should be competed as soon as possible after there is sufficient information to
- evaluate the event. All other reportable ADEs and other reportable AEs should be submitted by
- completion on the eCRF(s) within 7 days of the site becoming aware of the event.
- 787 The Sponsor will notify all participating investigators of any adverse event that is serious, related, and
- unexpected. Notification will be made within 10 working days after the Sponsor becomes aware of the
- 789 event.

802

803

804 805

806

780

- 790 Each principal investigator is responsible for reporting serious study-related adverse events and abiding
- by any other reporting requirements specific to his/her Institutional Review Board or Ethics Committee.
- Upon receipt of a qualifying event, the Sponsor will investigate the event to determine if a UADE has
- 793 occurred, and if indicated, report the results of the investigation to all overseeing IRBs, and the FDA
- within 10 working days of the Sponsor becoming aware of the UADE per 21CFR 812.46(b). The Sponsor
- must determine if the UADE presents an unreasonable risk to participants. If so, the Sponsor must ensure
- that all investigations, or parts of investigations presenting that risk, are terminated as soon as possible but
- no later than 5 working days after the Sponsor makes this determination and no later than 15 working
- days after first receipt notice of the UADE.
- 799 The investigators are also required to report, without unjustified delay, all device complaints and
- malfunctions that could have led to a UADE, including device complaints and malfunctions, irrespective
- of whether an adverse event occurred.

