6.6 Stopping Criteria

6.6.1 Participant Discontinuation of Study Device

- In the case of an unanticipated system malfunction resulting in a severe hypoglycemia or DKA event (or a malfunction that could have led to severe hypoglycemia or DKA), use of the study device will be suspended for that participant while the problem is diagnosed. The UADE will be reported to the IRB and FDA. After assessment of the problem and any correction, use of the study device will not be restarted
- until approval is received from the IRB and FDA.
- In the absence of a device malfunction, use of the study device by a participant will be discontinued if any of the following occur:
- The investigator believes it is unsafe for the participant to continue on the intervention. This could be due to the development of a new medical condition or worsening of an existing condition; or participant behavior contrary to the indications for use of the device that imposes on the participant's safety
- The participant requests that the treatment be stopped
- Participant pregnancy
- One distinct episodes of DKA in the study treatment period as defined in section 6.2.4
- One distinct severe hypoglycemia events in the study treatment period as defined in section 6.2.3
- Each DKA or severe hypoglycemia event will be reviewed by the Medical Monitor with respect to
- determination of cause and whether the occurrence of the event can be attributed to use of the study
- device or study drug.

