6.6.2 Criteria for Suspending or Stopping Overall Study

- In addition to the suspension of device use due to a UADE as described in section 6.6.1, study activities
- could be similarly suspended if the manufacturer of any constituent study device requires stoppage of
- device use for safety reasons (e.g. product recall). The affected study activities may resume if the
- underlying problem can be corrected by a protocol or system modification that will not invalidate the
- results obtained prior to suspension.
- Closed-loop system use will also be suspended if there are five or more cases of severe hypoglycemia or
- five or more cases of DKA across the entire study in participants who have initiated Control-IQ
- technology 2.0 use. The IRBs and FDA will be notified. After assessment of the problem and any
- corrections are implemented, use of the closed-loop system may be restarted if approval is received from
- the IRBs and FDA.

846

835

815

816

847	Chapter 7: Miscellaneous Considerations
848	7.1 Drugs Used as Part of the Protocol
849 850	Subjects will use their own Humalog (insulin lispro) or Novolog (insulin aspart) during the Run In and Treatment Period with the study devices.
851	7.2 Collection of Medical Conditions and Medications
852 853 854	Pre-Existing Conditions : Any medical condition that is either present at screening, a chronic disease, or a prior condition that could impact the participant's health during the course of the study (e.g., prior myocardial infarction or stroke) will be recorded.
855 856	Medical Conditions Developing During the Study : Medical conditions developing during the study will be reviewed by the investigator for their relationship to the study device.
857 858 859 860	Medications : All medications in use at the time of screening or added during the course of the study will be recorded. Nutraceuticals and preventative treatment also will be recorded. Medications only taken as needed either can be recorded when prescribed or only recorded if used during the study. Glucagon for treatment of severe hypoglycemia will only be recorded if used during the study.
861	7.3 Prohibited Medications, Devices, Treatments, and Procedures

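### The study-wide stopping count ignores cause, but the 1-working-day reporting deadline that should feed it depends on cause, so severe hypoglycemia and DKA cases judged unrelated may be counted about 4 to 6 days late

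*Combined protocol and SAP*

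**What the plan says.** **The stopping rule (6.6.2).** The SH limb begins "Closed-loop system use will also be suspended if there are five or more cases of severe hypoglycemia or", and the separate limb for DKA reads "five or more cases of DKA across the entire study in participants who have initiated Control-IQ"; the version meant is 2.0. The rule counts cases in participants who have begun 2.0 and sets no condition on relatedness.

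**The reporting deadlines (6.4).** "SAEs possibly related to a study device, study drug, or study participation and UADEs must be reported" to the sponsor within 1 working day of site awareness, by phone, email or eCRF. All remaining reportable events are due by "completion on the eCRF(s) within 7 days of the site becoming aware of the event". No separate deadline covers all SAEs.

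**Seriousness and default causality (6.2.3, 6.2.4).** "Severe hypoglycemia events should be considered to be serious adverse events with respect to" reporting requirements, and 6.2.4 says the same of DKA. Both sections add that such an event will ordinarily be classed as unrelated to the device when the device worked as designed and no design flaw is apparent.

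**Review (6.5, 6.6.1, 6.2.5).** "Each DKA or severe hypoglycemia event will be reviewed by the Medical Monitor with respect to" its cause and attribution. Section 6.5 says SAEs are typically reviewed within 1 working day, counted from reporting. Section 6.2.5 bases reporting requirements on the Medical Monitor's causality assessment rather than the investigator's.

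**The concern.** A count can be no more current than the reports that feed it. Section 6.6.2 needs every SH and DKA case after the start of 2.0. Section 6.4 guarantees prompt receipt only of cases thought possibly related to device, drug or participation. Calling these events serious for reporting purposes does not close the gap, because seriousness alone does not bring the fast deadline in 6.4.

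With up to 6 sites, no single site can know the study-wide total, so only central reporting can trigger 6.6.2. If the fifth case, or an earlier one needed to make up five, is on the slow route, other participants could remain on closed-loop use after the criterion has been met. SH and DKA are also the first two primary endpoints of a study whose stated purpose is safety.

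**Working it through.** The documents give no figure for reporting lag or for concurrent exposure, so there is nothing to reproduce. The check is a comparison of text followed by calendar arithmetic.

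**Step 1. Trace one case.** Take a participant on 2.0 with an SH or DKA event, a device that worked as intended, and a judgement of unrelated to device, drug and participation.

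| Question | Section | Answer |
|---|---|---|
| Is it an SAE for reporting? | 6.2.3, 6.2.4 | Yes |
| Does it add to the study-wide count? | 6.6.2 | Yes |
| Is it due in 1 working day? | 6.4 | No, unless it is a UADE |
| Is it due in 7 days? | 6.4 | Yes |
| When does the Monitor's review start? | 6.5 | At reporting, not at site awareness |

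**Step 2. Lag from site awareness to sponsor receipt.** Inputs are the two limits in 6.4, in calendar days, ignoring holidays. Avoidable lag = 7 − (calendar days taken by 1 working day).

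| Day of awareness | 1 working day | 7-day limit | Avoidable lag |
|---|---|---|---|
| Mon to Thu | 1 | 7 | 6 |
| Fri | 3 | 7 | 4 |
| Sat | 2 | 7 | 5 |
| Sun | 1 | 7 | 6 |

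The avoidable lag is 4 to 6 days. Adding 1 working day for the Monitor's review gives a total of 2 to 4 days on the fast route and 8 to 10 on the slow route. The day-by-day difference is again 4 to 6 days.

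**Step 3. Exposure during the avoidable lag.** The number on 2.0 at any one time is not stated; assume k = 10 to 30. Further use = k × avoidable lag:

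- lower end: 10 × 4 = 40 participant-days
- upper end: 30 × 6 = 180 participant-days

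**Step 4. What that exposure could mean (illustration only).** Assume an event rate just high enough to give five cases of one type over the planned completers' time on 2.0. That time is 72 participants × 28 days = 2,016 participant-days, and the rate is 5 / 2,016 per day. Expected further cases of that type are then 40 × 5 / 2,016 = 0.10 to 180 × 5 / 2,016 = 0.45. The true rate is unknown.

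**The case against.** **The slow route is residual.** The fast rule has three limbs: device, drug and study participation. Under 6.2.5 a possible relationship needs only a weak scientific basis, and the unrelated category requires a clear absence of relationship. The default in 6.2.3 and 6.2.4 concerns the device alone, so a case after a meal challenge could still qualify through participation. This stands: only cases judged unrelated on all three limbs have 7 days, and the documents do not show how many that would be. But the causality guidance in 6.2.5 covers device and drug only, so relatedness to participation is left undefined.

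**The Medical Monitor's view governs reporting (6.2.5).** One could read this as preventing a site from downgrading a case on its own. Section 6.4 does not say whose judgement starts the clock, so the point is open. In practice the Monitor, who is the sponsor's Medical Director, cannot assess an event before hearing of it.

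**Sites may call sooner.** They may; 7 days is a ceiling. Section 6.5 also mentions a safety management plan, in connection with adjudication, that is not among the documents. The real-time CGM alerts in 3.9 do not fill the gap. They cover the first ten 6-13 year olds starting the lower target, for one week, and all 2-5 year olds, and they go to study staff providers.

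**Stronger readings a reader might infer.**

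- *That the participant-level rule in 6.6.1 is also delayed.* It is not. Its criteria, "One distinct episodes of DKA in the study treatment period as defined in section 6.2.4" and "One distinct severe hypoglycemia events in the study treatment period as defined in section 6.2.3", need no central count, so the site can act on awareness.
- *That preschool enrollment could open on an out-of-date count.* Section 2.1 does refer to the stopping criteria, but through a documented review that includes the site primary investigators and needs all parties' approval. Those holding any unreported case are in the room, so this step is largely protected.

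**Conclusion.** The mismatch holds for the study-wide count in 6.6.2. An SH or DKA case in a participant who has started 2.0, judged unrelated to device, drug and participation, counts towards suspension but need not reach the sponsor for up to 7 days after site awareness. Nothing else in the documents sends it sooner.

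The count could run about 4 to 6 calendar days later than under the 1-working-day rule. That corresponds to about 40 to 180 participant-days of further use, on two conditions: 10 to 30 participants are on 2.0 at once, and a late report delays recognition of the fifth case. If fewer than five cases of either type occur, the lag has no effect on suspension.

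A reader might take the whole 7 days as lost time, or express it as half of a 14-day target period. Neither is supported. The fast rule itself takes 1 to 3 calendar days, and the participant who had the event comes off the device under 6.6.1, so a share of that person's exposure does not measure the harm. Nor do all SH and DKA cases fall on the slow route. The gap is limited, but it affects a stated safety rule and is cheap to close.

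**What to change.** In 6.4, add that every event meeting the SH definition in 6.2.3 or the DKA definition in 6.2.4 is reported to the sponsor within 1 working day of site awareness, regardless of its assessed relationship to device, drug or participation. State that the 6.6.2 count uses these reports. Keep the 7-day limit for all other reportable ADEs and AEs not already under the 1-working-day rule. Wording that kept 7 days only for non-serious events would leave other unrelated SAEs, such as an unrelated hospitalization, with no deadline.

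The cost is a few more expedited reports from sites. These events already require an adverse event form, and 6.4 already accepts phone or email as first notice. With this change the longest lag to sponsor receipt falls from 7 calendar days to between 1 and 3. The stopping thresholds and the causality process stay as they are.
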